OTC	Over-the-counter
PRO	Patient-reported outcomes
QOL	Quality of life
QTcF	QT interval corrected using Fridericia's Formula
SAE	Serious adverse event
SC	Subcutaneously
SD	Standard deviation
TB	Tuberculosis
TEAE	Treatment-emergent adverse event
TNF- α	Tumor necrosis factor- alpha
U	Units
ULN	Upper limit of normal
US	United States
VAS	Visual Analogue Scale

SYNOPSIS

Study Title: A Multicenter, Open-label Study to Assess the Efficacy and Safety of Acthar® Gel in Subjects with Severe Keratitis	
Protocol Number: MNK14084113	Type: Interventional/Phase 4
Condition/Disease: Severe or Recalcitrant Keratitis	
Approximate Number of Subjects: Up to 36 subjects enrolled	Approximate Duration of Subject Participation: 22 weeks
Approximate Number of Study Centers: 6	Approximate Duration of Study: 1 year

Rationale:

Noninfectious keratitis can result from many different etiologies including systemic autoimmune disorder. Inflammatory cells express melanocortin receptors (MCRs) and anecdotal evidence suggests that adrenocorticotropic hormone (ACTH) gel, a MCR agonist, is beneficial in treating ocular inflammation and alleviating the associated symptoms (Perez, 2019). Acthar is believed to exert its effect through the activation of multiple MCRs present in immune cells, as well as in the eye, and the induction of cortisol in the adrenocortex. The introduction of Acthar to the treatment algorithm for keratitis may provide a treatment option when early treatments have failed or were not well tolerated. The study is being conducted to explore the efficacy and safety of Acthar in subjects with severe keratitis to better understand how different clinical parameters observed within the spectrum of this condition might be impacted by treatment with Acthar® Gel.

Objectives and Endpoints:

To evaluate the safety and efficacy of Acthar in subjects with severe keratitis when treated with Acthar gel. Efficacy endpoints include corneal staining, conjunctival staining, conjunctival redness, tear production, tear film stability, dryness, ocular discomfort, grittiness, burning, stinging, Quality of Life, and cytokine array levels. Safety endpoints include the incidence and severity of ocular adverse events (AEs), incidence and severity of other AEs, new or worsening cataracts, and the mean change in intraocular pressure (IOP).

Outcome Measures:

Primary: The proportion of responders who improved on the IDEEL score.

Secondary: Not applicable.

Overall Design:

This is a multicenter, multiple dose, open-label study to examine the efficacy of Acthar in adult subjects 18 years of age or older with a diagnosis of keratitis sicca. Up to 36 subjects with severe or recalcitrant keratitis who did not respond or tolerate treatment with topical cyclosporine or any immunosuppressant to treat keratitis will be enrolled. Subjects who meet entry criteria will be treated with Acthar 1 mL (80 units [U]) subcutaneously (SC) 2x (twice) per week for 12 weeks. After this 12 weeks, Acthar will be tapered over 4 weeks. The 80 U dose will be reduced to 40 U 2x/week for 2 weeks, followed by 40 U 1x/week for 2 additional weeks. Subjects will be reassessed at an in-clinic

Study Title: A Multicenter, Open-label Study to Assess the Efficacy and Safety of Acthar® Gel in Subjects with Severe Keratitis

Protocol Number: MNK14084113 Type: Interventional/Phase 4

Condition/Disease: Severe or Recalcitrant Keratitis

safety visit, 4 weeks after the last treatment dose for AE assessments and concomitant medication use. Endpoints will be measured at Baseline (Visit 2 [Day 1]), and Visit 3 through 6.

Number of Subjects:

Up to 36 subjects will be enrolled in this study at approximately 6 sites in the US.

Treatment Groups and Duration:

Subjects with severe or recalcitrant keratitis who did not respond or tolerate treatment with topical cyclosporine or any immunosuppressant to treat keratitis will be enrolled. Subjects will participate in the study for approximately 22 weeks, including a screening period of up to 28 days, an active treatment period of 12 weeks, an Acthar taper period of 4 weeks, and a follow up in-person safety visit 4 weeks after the last dose of study drug.

SCHEDULE OF STUDY EVENTS

Table 1: Schedule of Study Events

Study procedures	Visit 1 Screening Day -28 to-1	Visit 2 Baseline Day 1	Visit 3 Phone Day 15 ±1	Visit 4 In Clinic Day 29 ±2	Visit 5 In Clinic Day 43 ±2	Visit 6 In Clinic Day 85 ±3	Visit 7 In Clinic / End of Acthar Taper Day 113 ±3	Early Termination
Informed consent	X							
Urine pregnancy test	X							
Demographic data, medical, surgical, ophthalmic history	X							
Patient-Reported Outcomes								
ODS	X	X		X	X	X		X
IDEEL and VAS		X	X	X	X	X		X
Ophthalmic examination								
Visual Acuity	X	X		X	X	X	X	X
Slit Lamp Evaluation	X	X		X	X	X	X	X
Conjunctival redness	X	X		X	X	X		X
Tear film breakup time	X	X		X	X	X		X
Inferior corneal staining score	X	X		X	X	X		X

Study procedures	Visit 1 Screening Day -28 to-1	Visit 2 Baseline Day 1	Visit 3 Phone Day 15 ±1	Visit 4 In Clinic Day 29 ±2	Visit 5 In Clinic Day 43 ±2	Visit 6 In Clinic Day 85 ±3	Visit 7 In Clinic / End of Acthar Taper Day 113 ±3	Early Termination
Superior, central and total corneal staining score (fluorescein)	X	X		X	X	X		X
Nasal, temporal and total conjunctival staining score (lissamine green)	X	X		X	X	X		X
Schirmer's Test	X	X		X	X	X		X
IOP	X					X	X	X
Undilated Fundoscopy	X					X	X	X
Inclusion/Exclusion criteria review	X	X						
Height ^a and weight	X	X				X	X	X
Vital signs ^b	X	X		X	X	X	X	X
Physical examination	X					X		X
Laboratory testing								
Chemistry and others ^c	X	X		X	X	X		X
HbA1c	X	X		X	X	X		X
Serum Pregnancy	X	X		X	X	X		X

Study procedures	Visit 1 Screening Day -28 to-1	Visit 2 Baseline Day 1	Visit 3 Phone Day 15 ±1	Visit 4 In Clinic Day 29 ±2	Visit 5 In Clinic Day 43 ±2	Visit 6 In Clinic Day 85 ±3	Visit 7 In Clinic / End of Acthar Taper Day 113 ±3	Early Termination
Hepatitis Serology ^d	X							
IGRA for TB	X							
Immunological protein assay ^e	X	X				X		X
IXRS contact	X	X		X	X			X
Study Therapy								
Study drug and injection record training		X						
Dispense study drug		X		X	X			
Administer first dose in clinic ^f		X						
Adverse event assessment	X	X	X	X	X	X	X	X
Injection record review				X	X	X	X	X
Concomitant treatment review		X	X	X	X	X	X	X
Start Acthar Taper						X		
End Acthar Taper							X	
Study exit							X	X

AE = adverse events; ET = early termination; HbA1c = glycosylated hemoglobin; IDEEL = Impact of Dry Eye on Everyday Life; IGRA = Interferon gamma release assay; IOP = Intraocular Pressure; ODS = Ocular Discomfort Score; TB = tuberculosis; VAS = Visual Analogue Scale.

^a Height at screening only. Weight at screening, Visits 2, 6, and ET.

^b Blood pressure, respiratory rate, pulse rate and body temperature. For blood pressure, an average of 2 readings after the subject has been seated for \geq 5 minutes at the Screening and Baseline Visits. Single readings after subject has been seated for \geq 5 minutes at all other time points.

^c Refer to Section 9.2.

^d HBsAg, HBcAb, and HCV.

^e Refer to Table 2.

^f The first dose will be administered at the clinic and the subject should be observed for at least 1 hour after dosing.

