3. STUDY DESIGN

3.1. Overall Design

This is a multicenter, multiple dose, open-label study to examine the efficacy of Acthar in adult subjects 18 years of age or older with a diagnosis of keratitis sicca. Up to 36 subjects with severe or recalcitrant keratitis who did not respond or tolerate treatment with topical cyclosporine or any immunosuppressant to treat keratitis will be enrolled. Subjects who meet entry criteria will be treated with Acthar 1 mL (80 units [U]) subcutaneously (SC) 2x (twice) per week for 12 weeks, followed by a 4 week taper period of 40 U 2x/week for 2 weeks then 40 U 1x/week for 2 more weeks. Subjects will be reassessed at an in-clinic safety visit, 4 weeks after the last treatment dose for AE assessments, and concomitant medication use. Endpoints will be measured at Baseline and all other visits.

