3.2. Duration of Subject Participation

Subjects will participate in the study for approximately 22 weeks, including a screening period of up to 28 days, an active treatment period of 12 weeks, an Acthar taper period of 4 weeks, and a follow up in-person safety visit 4 weeks after the last treatment dose of study drug.

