3.6. End of Study Definition

A subject is considered to have completed the study if the subject has completed the final assessments at Visit 7.

The end of the study is defined as the completion of the final assessment for the last subject enrolled in the trial.

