5.1. Treatment Administration

Following a screening period of up to 28 days, subjects who meet entry criteria will be treated with Acthar 1 mL (80 units [U]) subcutaneously (SC) 2x (twice) per week for 12 weeks. After this 12 week period of treatment with 80 U, Acthar will be tapered over a 4 week period. The 80 U dose will be reduced to 40 U 2x/week for 2 weeks, followed by 40 U 1x/week for 2 additional weeks. An in-clinic safety visit will also take place 4 weeks after the last treatment dose. The subject or subject's caregiver will receive training/instructions and will administer the first dose of study drug in the clinic under the supervision of study staff. The subject will remain in the clinic for at least 1 hour postdose to monitor for allergic, including anaphylactic, reactions. Thereafter, all doses will be administered by the subject or the subject's caregiver at home. If a subject misses a dose, that dose will be skipped and the reason for the missed dose will be recorded.

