5.6. Prior and Concomitant Therapy

The start and stop date, dose, unit, frequency, route of administration, and indication for all prior (taken within the 30 days prior to the Screening Visit) and concomitant (taken from the Screening Visit through Visit 7) medications and nondrug therapies (eg, blood transfusions, oxygen supplementation, physical therapy, etc) received will be recorded.

In addition, all prior treatments for severe keratitis administered be recorded with start and stop date, dose, unit, frequency and route of administration.

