5.6.2. Prohibited Concomitant Therapies

The following treatments will not be permitted during the study (from the Baseline Visit through Visit 7):

- Administration of live or live-attenuated vaccines.
- Use of eyelash growth medications.
- Topical, inhaled, intra-articular, or intra-ocular corticosteroids.
- Any systemic corticosteroids, immunosuppressants, immunomodulators, or biologic agents for a concomitant condition (eg, rheumatoid arthritis being treated with a TNF- α drug).
- Any investigational drug, device, or procedure administered as part of a research study.

If any prohibited medication is taken during the study, all pertinent information will be recorded in source documents and the electronic case report form (eCRF). The designated study medical monitor (MM) must be informed immediately and will determine whether to continue the subject in the study in collaboration with the sponsor.

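### The in-clinic safety visit promised 4 weeks after the last dose is missing from Table 1, so AE recording ends at an unscheduled visit that conflicts with study exit at Visit 7

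*Combined protocol and SAP*

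**What the plan says.** **The visit is promised in the text.** The synopsis (Treatment Groups and Duration) lists screening, 12 weeks of active treatment, a 4-week taper, and then "a follow up in-person safety visit 4 weeks after the last dose of study drug". Section 3.2 gives the same list and ends with "a follow up in-person safety visit 4 weeks after the last treatment dose of study drug". Section 3.1 says "Subjects will be reassessed at an in-clinic safety visit, 4 weeks after the last treatment dose for AE assessments, and concomitant medication use". Section 5.1 describes the taper and then adds "An in-clinic safety visit will also take place 4 weeks after the last treatment dose". Section 9.3.4 has AEs and SAEs recorded from consent until a Follow-up Visit is complete, and gives that visit no number, day or window.

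**The schedule stops earlier.** The last scheduled column of Table 1 is "Visit 7 In Clinic / End of Acthar Taper Day 113 ±3". The only column after it is Early Termination, and study exit is marked under those two alone. Section 3.6 states: "A subject is considered to have completed the study if the subject has completed the final assessments at Visit 7". Section 5.6 defines concomitant medications as those "taken from the Screening Visit through Visit 7". Section 5.6.2 lists treatments that "will not be permitted during the study (from the Baseline Visit through Visit 7").

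**Contraception.** Inclusions 7 and 8 in Section 4.1 require it for the study's duration, with Visit 6 given in brackets as the end point. Section 7.2.5 documents agreement for the whole of participation plus 28 days. Table 1 starts the taper at Visit 6.

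**The concern.** A site working from Table 1 and Section 3.6 would discharge each completer at the end of the taper and never hold the visit that the text promises. The rule that ends AE recording points to that same visit, so the rule and study exit cannot both be followed.

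What is at stake is the scheduled detection of events that begin once the drug has stopped. Section 9.3.2 lists events associated with withdrawal of study drug among its examples of AEs. The incidence of ocular and other AEs is a stated safety endpoint, and Section 9.1.5 provides for no monitoring committee.

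The contraception wording is a separate and smaller matter. Its bracketed end point falls before the study ends and before the taper doses are given, so a site could apply the shorter rule.

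**Working it through.** **Inputs.** Day 1 is the first dose and there is no Day 0. The 80 U phase lasts 12 weeks. The taper is 40 U twice weekly for 2 weeks, then once weekly for 2 weeks (Section 5.1). Visit 6 is Day 85 ±3 and Visit 7 is Day 113 ±3 (Table 1). Assumptions: the taper starts at Visit 6, and the last weekly dose may fall on any day of the fourth taper week.

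**1. The plan's own duration of about 22 weeks**
- Listed components with maximum screening: 4 + 12 + 4 + 4 = 24 weeks. Without the follow-up visit: 4 + 12 + 4 = 20 weeks.
- By calendar, exit at Visit 7: (113 − 1 + 28)/7 = 20.0 weeks, or (116 − 1 + 28)/7 = 20.4 at the late edge of the window.
- By calendar, exit at the promised visit (days from step 2): (134 − 1 + 28)/7 = 23.0 to (140 − 1 + 28)/7 = 23.9 weeks.
- The stated 22 is not reproduced at maximum screening. With the follow-up visit included, a 2-week screening period (assumed) gives 2 + 12 + 4 + 4 = 22.

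**2. Nominal calendar**
- Taper start: 1 + 84 = Day 85. Taper end: 85 + 28 = Day 113.
- Last taper dose: 85 + 21 to 85 + 27 = Day 106 to 112.
- Visit 7 after the last dose: 113 − 112 to 113 − 106 = 1 to 7 days.
- Promised visit: 106 + 28 to 112 + 28 = Day 134 to 140, which is 21 to 27 days after Visit 7.

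**3. Could the visit windows close the gap?**
- Visit 6 on Day 82 puts the earliest final dose on 82 + 21 = Day 103. With Visit 7 on Day 116 the lag is 116 − 103 = 13 days, still 15 short of 28.
- If the final weekly dose is also skipped, the earliest last dose is 82 + 14 = Day 96, and the lag is 116 − 96 = 20 days.
- Visit 7 does not reach 28 days off drug in either case.

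**4. Length of the AE window under the two end points**
- From Day 1: 112 days to Visit 7, against 133 to 139 days to the promised visit. The difference is 21/112 = 19% to 27/112 = 24%.
- From consent with a full 28-day screening: 140 days to Visit 7. The difference is 21/140 = 15% to 27/140 = 19%.
- These are differences in calendar time, not in AE incidence.

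**5. Contraception**
- Taper doses: 2×2 + 2×1 = 6, all at or after Visit 6.
- Section 7.2.5 period if participation ends at Visit 7: 113 + 28 = Day 141, which is 56 days past Visit 6.
- If participation ends at the promised visit: 134 + 28 to 140 + 28 = Day 162 to 168, which is 77 to 83 days past Visit 6.

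**The case against.** The best defence is that Visit 7 is the safety visit. The protocol separates a 12-week active treatment period from the taper, so the last treatment dose could mean the last 80 U dose, and Day 113 is exactly 28 days after Day 85. Visit 7 also looks like a safety visit: it has AE and concomitant treatment review, IOP, slit lamp, fundoscopy and vital signs, but no symptom questionnaires, staining or Schirmer's test. Sections 3.6, 5.6 and 5.6.2 and the study exit row all agree on Visit 7.

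This is a possible account of what the sponsor intended, but the text does not bear it out. The synopsis counts from the last dose of study drug, which the taper doses are. The synopsis and Section 3.2 list the follow-up visit as a separate item after the taper, and Section 5.1 introduces it as an additional visit. A stated participation of about 22 weeks also exceeds the 20.4-week maximum to Visit 7, although an approximate figure can only support the point. If the sponsor did mean Visit 7, those sections are wrong and still need correcting.

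A reader might infer more than the documents support:
- *That the AE cut-off is undefined.* Section 9.3.4 does name one. The fault is that the named visit is unscheduled and conflicts with study exit.
- *That ongoing AEs are closed or lost.* Section 9.3.3 leaves the stop date of an ongoing event blank. Sections 7.3, 9.3.4 and 9.3.5 provide for follow-up of events already present.
- *That the treatment-emergent definition in Section 8.3.2 is deficient because it has no end date.* Section 8.3 is a general summary that defers detail to a separate SAP, where such a date normally belongs.
- *That sites will in fact collect AEs over different periods.* The conflict makes this possible. One schedule and sponsor monitoring apply to every site, so the documents do not show that it will happen.

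**Conclusion.** The text and the schedule contradict each other, and the contradiction should be fixed. Four parts of the protocol promise an in-clinic safety visit 4 weeks after the last dose and Section 9.3.4 relies on a follow-up visit, while Table 1 and Section 3.6 end the study 1 to 7 days after the last taper dose. Allowing for stretched windows and one skipped final dose, the lag is at most 20 days, so Visit 7 cannot stand in for the promised visit. The check that would be missed falls 21 to 27 days after Visit 7. This rests on the taper starting at Visit 6, as Table 1 marks, and on no more than the final weekly dose being skipped.

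The consequence is limited to safety follow-up. Completers would have no scheduled contact after Visit 7 to detect new events off drug. The safety analysis is descriptive and single-arm, and the IDEEL primary outcome is not affected. The 22-week figure is approximate, with screening of up to 28 days, and is not treated as an error.

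The contraception wording is a separate, smaller correction: it contradicts itself and Section 7.2.5, and adds no weight to the main point.

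**What to change.** 1. Add a column to Table 1 about 28 days after the last taper dose (about Day 134 to 140), with AE and concomitant medication review.
2. Name that visit as the Follow-up Visit in Section 9.3.4, and bring Section 3.6, Section 5.6 and the study exit row into line. State whether it also applies after Early Termination.
3. Leave the prohibited-therapy period in Section 5.6.2 ending at Visit 7. Extending it would bar subjects who have stopped Acthar from topical corticosteroids for another 3 to 4 weeks.
4. In Inclusions 7 and 8, replace the bracketed Visit 6 limit with the period in Section 7.2.5.

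If the sponsor meant Visit 7 to be the safety visit, correct the synopsis and Sections 3.1, 3.2 and 5.1, name Visit 7 in Section 9.3.4, and say openly that there is no scheduled check 4 weeks off drug. That removes the contradiction but not the gap in follow-up.

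The cost is one protocol amendment and one short visit per subject (up to 36), which the text already promises. Each subject stays on study 3 to 4 weeks longer than Table 1 shows. Contraception runs to about Day 162 to 168 if participation ends at the new visit. The efficacy analysis does not change.

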1. BACKGROUND INFORMATION AND RATIONALE

1.1. Disease/Condition Under Study

Keratitis is a painful inflammation of the cornea which can result in partial or total loss of vision if left untreated and is a significant cause of ocular morbidity around the world ([Sharma, 2001](#)). It can result from infectious agents (eg, microbes including bacteria, fungi, amebae, and viruses) ([Collier, 2010](#)) or from noninfectious causes (eg, eye trauma, chemical exposure, and ultraviolet exposure). Conditions that affect the integrity of the ocular surface epithelium (exposure keratitis, neurotrophic keratitis, keratomalacia, recurrent corneal erosions) may also lead to development of sterile corneal ulcers. Non-infectious corneal ulcers may be associated with various collagen vascular or other autoimmune diseases, sometimes as the presenting sign of the disease ([Donzis, 1987](#)).

As described in the Package Insert, Acthar® Gel (repository corticotropin injection, hereafter referred to as Acthar) is a naturally sourced complex mixture of adrenocorticotrophic hormone (ACTH) analogues and other pituitary peptides (Mallinckrodt Package Insert, 2019) currently approved for the treatment of ocular inflammatory conditions including keratitis. ACTH is a member of the family of structurally related peptides known as melanocortin peptides.

Melanocortin peptides, which include ACTH, as well as, α -, β -, and γ -melanocyte stimulating hormones, are derived from the natural protein pro-opiomelanocortin and exert their physiologic effects by binding to cell surface G-protein coupled receptors known as melanocortin receptors (MCRs) ([Mountjoy, 1992](#)). Five subtypes of MCRs have been identified to date (MC1R to MC5R), each with different tissue distributions, binding affinity characteristics, and physiological roles ([Getting, 2006](#)) ([Montero-Melendez, 2015](#)). ACTH binds to all 5 subtypes of MCR ([Schioth, 1995](#)).

A detailed description of the chemistry, pharmacology, efficacy, and safety of Acthar is provided in the ([Acthar® Gel Package Insert, 2019](#))

1.2. Study Rationale

Noninfectious keratitis can result from many different etiologies including systemic autoimmune disorder. Inflammatory cells express melanocortin receptors (MCRs) and anecdotal evidence suggests that Acthar Gel, a MCR agonist, is beneficial in treating ocular inflammation and alleviating the associated symptoms ([Perez, 2019](#)). Acthar is believed to exert its immunomodulatory effect through the activation of multiple MCRs present in immune cells, as well as in the eye, and the adrenocortex. The introduction of Acthar to the treatment algorithm for keratitis may provide a treatment option when early treatments have failed or were not well tolerated.

The study is being conducted to explore the efficacy and safety of Acthar in subjects with severe keratitis to better understand how different clinical parameters observed within the spectrum of this condition might be impacted by treatment with Acthar® Gel.

1.3. Assessment of Potential Benefits and Risks

Common adverse reactions for Acthar include fluid retention, alteration in glucose tolerance, elevation in blood pressure, behavioral and mood changes, increased appetite, and weight gain.

Prolonged use of Acthar may produce posterior subscapular cataracts, glaucoma with possible damage to the optic nerves, and may enhance establishment of secondary ocular infections due to fungi and viruses. For a complete reference of known potential risks, refer to the [**Acthar® Gel Package Insert, 2019**](#). More detailed information about the known and expected benefit, risks, and reasonably expected adverse events (AE) can be found in the Acthar® Gel Package Insert, 2019.

